Among AF patients with guideline indications for OAC for stroke prevention who have not received any OAC dispensing for at least one year, an education intervention at the patient-level and the provider-level will increase the proportion of patients started on OAC for stroke prevention.

IV. STUDY RATIONALE

Preliminary data from three Sentinel Data Partners between 1/1/2006 and 6/30/2015, identified 231,696 patients (1.4%) with at least 2 diagnoses of AF (ICD-9 codes of 427.31 or 427.32) over the study period, among 16.2 million covered lives. Within the 231,696 AF patients, there were 201,882 with a CHA₂DS₂-VASc score of 2 or greater (based on administrative claims data in the Sentinel Distributed Database), which is an American Heart Association (AHA)/American College of Cardiology (ACC) guideline indication for OAC. Over the study period from 2006 through 2015, 52% (n=105,256) patients filled at least one prescription for anticoagulation, meaning that 48% of patients with CHA₂DS₂-VASc score of 2 or greater never had a pharmacy claim submitted for an OAC during the study period. While there may be clinical or health system related reasons for not treating some of these patients, this apparent significant gap of guideline-based adherence is a public health issue of interest. The presented protocol is an opportunity to test the potential for developing and testing a health plan (Data Partner) based education intervention to improve the quality of care.

V. STUDY OBJECTIVES

A. PRIMARY OBJECTIVE

The primary objective is to evaluate the effect of the patient and provider education interventions (versus usual care with delayed provider education intervention) on the proportion of patients with evidence of at least one OAC prescription fill (defined as one OAC dispensing or 4 INR tests) over the course of the follow-up through the date on which at least 80% of eligible study participants have at least 12 months of follow-up time.

B. SECONDARY OBJECTIVE

The secondary objectives are to evaluate the impact on outcomes of the patient and provider education interventions over the course of the follow-up through the date on which at least 80% of eligible study participants have at least 12 months of follow-up time:

- 1. Incident rate of stroke or transient ischemic attack (TIA) hospitalization
- 2. Incident rate of hospitalization for stroke
- 3. Time to first OAC prescription fill
- 4. Proportion of days covered by OAC prescription fills

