- 2. Time to OAC start: the time to first OAC initiation, as defined by the first fill date for apixaban, dabigatran, edoxaban, rivaroxaban, or warfarin. If there was no prescription fill for these medications, but the patient had 4 or more INR values measured over the study period, the date of the first INR measurement will be used for initiation of OAC.
- 3. OAC prescription coverage: the proportion of days that AF patients have OAC prescription fills over the duration of the study. The assumption is that a 30-day or 90-day supply will last for the planned period, even in the case of warfarin, when the length of time that a prescription lasts may be less well defined. Patients will only be included in this secondary analysis, if they had a prescription fill for apixaban, dabigatran, edoxaban, rivaroxaban, or warfarin.
- 4. OAC rates at follow-up: proportion of patients with an active oral anticoagulant dispensing at the end of the one-year follow-up. This will include patients with apixaban, dabigatran, edoxaban, rivaroxaban, or warfarin medication fills that encompass the end of the study period. If there was no prescription fill for these medications, this will also include patients with 4 or

more INR values measured over the study period, who had an INR value measured within 60 days of the end of the approximately one-year follow-up.

- 5. Rate of stroke or TIA: the incident rate of stroke or TIA related hospitalizations; stroke, excluding transient ischemic attacks (TIAs), will also be assessed
- 6. Rate of bleeding related hospitalization: the incident rate of hospitalizations for any bleeding
- 7. Health care utilization: the total counts of health care utilization (number of outpatient visits, emergency department visits, hospital admissions, etc.) for AF patients, including AF and non-AF related care
- 8. In-patient all-cause mortality: patients with in-hospital death
- 9. All-cause mortality: in a subset of patients with mortality status

XVI. STATISTICAL ANALYSES

A. DEMOGRAPHICS AND BASELINE CHARACTERISTICS

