5. Health Care Utilization	177
III. REFERENCES	188
IV. APPENDIX	199
A. TABLES.....	199
B. CONSORT 2010 WORKSHEET FOR RANDOMIZED TRIALS.....	33
C. ICD-10 CODES FOR DEFINING CLINICAL OUTCOMES	3735
D. ANALYSIS METHODS FOR DISTRIBUTED NETWORKS	39
1. Meta-analysis	39
2. Case-centered Logistic Regression	39
3. Distributed Regression	39

I. OVERVIEW

This is the statistical analysis plan (SAP) for **IM**plementation of a randomized controlled trial to im**Pr**ove treatment with oral **AntiCoagulanTs** in patients with **A**trial **F**ibrillation (IMPACT-AFib) study. The purpose of this document is to provide an overview of the study design and study objectives, outline the types of analyses and data presentations relevant to the study objectives, and to provide a detailed description of the methods in which the statistical analyses will be conducted to meet protocol objectives. This plan is a supplement to the materials provided in the IMPACT-AFib protocol. This SAP does not contain all the protocol details and is intended to be read in conjunction with the full protocol. Only analytic decisions are documented here.

A. PRIMARY ENDPOINT

IMPACT-AFib is a prospective randomized controlled clinical trial that will evaluate whether a patient and provider education intervention increases the proportion of patients with atrial fibrillation (AF) who fill at least one oral anticoagulant (OAC) over the course of follow-up. Follow up is through the date on which at least 80% of eligible study participants have at least 12 months of follow-up time. As described in the protocol, there is an “early intervention” arm (who receive patient and provider mailings) and a “delayed intervention” arm (who receive provider mailings only, ~12 months after the early intervention mailings occur).

B. SECONDARY ENDPOINTS

We will evaluate the impact of the patient and provider education intervention on the endpoints listed below at the end of follow-up (i.e., the date on which at least 80% of eligible study participants have at least 12 months of follow-up time):

- The incidence rate of stroke or transient ischemic attack (TIA) hospitalizations
- The incidence rate of stroke hospitalizations
- The time to first OAC prescription fill
- The proportion of days covered by OAC prescription fills
- Proportion of patients actively on OAC at 12 months of follow-up
- The incidence rate of hospitalization for any bleeding
- All-cause in-hospital mortality rates¹

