6. Patients with recent P2Y12 antagonist use (i.e., clopidogrel, prasugrel, or ticagrelor within 90 days of prior to randomization)

F. STUDY DESIGN AND DURATION

As described in detail in the protocol, the study is a prospective, randomized, and open-label educational intervention trial. Patients with AF and a CHA₂DS₂-VASc score of 2 or greater were randomized in a 1:1 ratio to an early intervention cohort and a delayed intervention cohort within each participating health plan. The definition for OAC medication fill was an OAC medication dispensing or at least 4 INR tests in the claims data.³ The claims records of the patients randomized to the early intervention cohort were then linked to “fresh” (i.e., about 1 month old) pharmacy claims data at the time of randomization. Patients without evidence of an OAC medication fill during the 12 months prior to randomization were included in the patient-level and provider-level early educational intervention (patients randomized to this early intervention with evidence of an OAC medication fill during the 12 months prior to randomization were excluded from the trial). In addition to usual care, these patients and their providers received a one-time mailing at trial start. There were two waves of mailing for the early intervention cohort at most sites due to the practical challenges of claims data: the patients were assigned to wave 1 if they had a provider easily identified in the data (i.e., the provider associated with the most recent AF diagnosis is indeed an individual provider), and they were assigned to wave 2 if it was difficult to identify a provider (e.g., the first identified provider is actually a facility). Follow-up time started on the date of the respective wave 1 and wave 2 mailings for the early intervention patients.

The delayed intervention cohort will have received usual care over the initial study period. After the date on which at least 80% of all eligible study participants have at least 12 months of follow-up time, the treatment status of the delayed intervention group will be assessed via the Sentinel data available at that time, in addition to “fresh” pharmacy claims data. The providers of patients in the delayed cohort who did not receive OAC medication during the course of follow-up and still meet all inclusion criteria will receive the provider-only education intervention (patients will not receive the educational materials unless no provider can be identified for a mailing).

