1. 33% OAC initiation rate in the delayed intervention arm
2. 38% OAC initiation rate in the early intervention arm (5% absolute improvement in OAC initiation over the 33% OAC initiation expected in the delayed intervention arm over 1-year follow-up)
3. 1-year attrition rate: 30% dropout or lost-to-follow-up
4. Two-sided type I error rate of 0.05
5. Roughly 10,000 patients who meet the inclusion/exclusion criteria will yield more than 99% power to detect a 5% absolute difference

Power	Total sample size (2-arm)	Early Intervention	Delayed Intervention
90%	5610	2805	2805
95%	6910	3455	3455
99%	9718	4859	4859

2. Important Secondary Outcome of Stroke or TIA

A study with approximately 80,000 patients could provide reasonable power for stroke or TIA outcome under certain assumptions listed below:

- 1-year stroke or TIA rate: 18% among patients not treated with OAC
- 1-year stroke or TIA rate: 7% among patients treated with at least 1 OAC fill
- Duration of follow-up: 1 year
- 33% of delayed intervention patients will have at least 1 fill of OAC, meaning the 1-year stroke or TIA rate in the delayed intervention group would be 14.4%
- 1-year attrition rate: 30% dropout or lost-to-follow-up
- Two-sided type I error of 0.05
- If 38% of early intervention patients have at least 1 fill of OAC (meaning the 1-year stroke or TIA rate in the early intervention group would be 13.82%, i.e., an absolute reduction of 0.55%), the study will have 46% power to detect this 0.55% reduction. However, if 40.5% of early intervention patients have at least 1 fill of OAC (meaning the 1-year stroke or TIA rate in the

early intervention group would be 13.54%, i.e., an absolute reduction of 0.83%), the study will have 80% power to detect this 0.83% reduction.

8. The sample size has 80% power to detect a 0.5% absolute reduction in stroke, assuming a cumulative 1-year incidence of stroke of 4.2% in control (delayed intervention arm) patients and 3.7% in intervention (early intervention arm) patients. The assumption is that patients not on oral anticoagulation have an annual stroke rate of 5%, and stroke will be reduced by 50% (HR=0.5) in the treated (anticoagulated) population. The 80% power requires that 52% of early intervention arm patients are treated at 1-year as compared to 33% in the control arm.

II. STATISTICAL ANALYSIS

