The proportion of patients actively on OAC at the end of follow-up will be summarized and compared between the early intervention and delayed intervention arms. Last Observation Carried Forward will be used if the patient is censored. To evaluate whether the early patient-level and provider-level educational intervention increases the proportion of patients being actively on OAC at the end of follow-up, we will calculate the odds ratio (i.e., the odds of an average patient in the early intervention group being actively on OAC at the end of follow-up as compared to the odds of an average patient in the delayed intervention group being actively on OAC at the end of follow-up) using logistic regression model adjusted for baseline risk factors listed in Appendix A Table A, with GEE to account for the correlation of responses among the patients from a same service provider. The odds ratio, 95% confidence interval (CI) and p-value will be presented to show whether there is a statistically significant difference in the proportion of patients who are actively on OAC at the end of follow-up between the early intervention and delayed intervention groups. Each Data Partner will run the SAS program(s) distributed by HPHCI, developed with the statistical team at Duke DCC, to perform logistic regression analysis on their cohort of patients and return the parameter estimate (SE), estimated odds ratio, 95% confidence interval (CI) and p-value, shown in Table 6 in Appendix A (there will be one for each Data Partner), to HPHCI. Meta-analysis methods with inverse-variance weighting on log scale will be used to integrate the results and obtain the estimate of the overall odds ratio, 95% confidence interval and p-value for entire study population.

4. Clinical Outcomes

Claims data (ICD-10-CM codes used for defining these outcomes are listed in Appendix C) will be used to define the following clinical outcomes:

- Hospitalization for ischemic stroke or unknown stroke
- Hospitalization for TIA
- Hospitalization for systemic embolism
- Hospitalization for ischemic stroke, TIA or systemic embolism
- Hospitalization for hemorrhagic stroke
- Hospitalization for any bleeding
- Hospitalization for ischemic or hemorrhagic stroke
- Hospitalization for ischemic or hemorrhagic stroke or systemic embolism
- Composite of ischemic stroke, hemorrhagic stroke, and hospitalization for any bleeding
- All-cause in-hospital death

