Mean proportion of days on an OAC			
Standard deviation			
Median proportion of days on OAC (range across sites)			
25 th percentile			
75 th percentile			
Proportion in each arm with ≥80% of follow up time covered by an OAC episode			

Table 6. Proportion of patients actively on OAC at the end of follow-up among those treated for at least 1 day: early intervention vs. delayed intervention in the modified intention to treat (mITT) analysis

	Early Intervention, n/N (%)	Delayed Intervention, n/N (%)	Parameter Estimate (SE)	Odds Ratio (95% CI)	p-value
Actively on OAC at the end of follow-up					

Table 7. Cumulative incidence of clinical endpoints during all follow up: early intervention vs. delayed intervention in the modified intention to treat (mITT) analysis

With / without Principal Discharge Diagnosis (PDX) Flag	Outcomes	Early Intervention, n/N (%)	Delayed Intervention, n/N (%)	Early Intervention, Cumulative incidence (95% CI)	Delayed Intervention, Cumulative incidence (95% CI)	p-value
Principal Discharge Diagnosis (PDX Flag) Only	Hospitalization for ischemic stroke or unknown stroke					
	Hospitalization for transient ischemic attack					
	Hospitalization for systemic embolism					
	Hospitalization for ischemic stroke, TIA, or systemic embolism					

With / without Principal Discharge Diagnosis (PDX) Flag	Outcomes	Early Intervention, n/N (%)	Delayed Intervention, n/N (%)	Early Intervention, Cumulative incidence (95% CI)	Delayed Intervention, Cumulative incidence (95% CI)	p-value
	Hospitalization for hemorrhagic stroke					
	Hospitalization for ischemic or hemorrhagic stroke					
	Hospitalization for ischemic or hemorrhagic stroke or systemic embolism					
	Hospitalization for any bleeding					
	Composite of ischemic stroke, hemorrhagic stroke, systemic embolism and hospitalization for any bleeding					
Ignore Principal Discharge Diagnosis (PDX) Flag	Hospitalization for ischemic stroke or unknown stroke					
	Hospitalization for ischemic stroke or transient ischemic attack					
	Hospitalization for systemic embolism					
	Hospitalization for ischemic stroke, TIA, or systemic embolism					
	Hospitalization for hemorrhagic stroke					

With / without Principal Discharge Diagnosis (PDX) Flag	Outcomes	Early Intervention, n/N (%)	Delayed Intervention, n/N (%)	Early Intervention, Cumulative incidence (95% CI)	Delayed Intervention, Cumulative incidence (95% CI)	p-value
	Hospitalization for ischemic or hemorrhagic stroke					

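### Stroke or TIA hospitalization, the first secondary endpoint, has no outcome of its own in SAP II.D.4 or Table 8, and Appendix C codes TIA as ischemic stroke, so secondary endpoints 1 and 2 cannot be told apart

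*SAP*

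**What the plan says.** Both documents put this endpoint first among the secondaries. Protocol V.B opens with "Incident rate of stroke or transient ischemic attack (TIA) hospitalization" and SAP I.B with "The incidence rate of stroke or transient ischemic attack (TIA) hospitalizations". Protocol XV item 5 defines two separate outcomes: "the incident rate of stroke or TIA related hospitalizations; stroke, excluding transient ischemic attacks (TIAs), will also be assessed". Protocol XVI.C also heads its event list with stroke or TIA. SAP I.G.2 treats it as the important secondary outcome: "A study with approximately 80,000 patients could provide reasonable power for stroke or TIA outcome under certain assumptions listed below".

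SAP II.D.4 then lists ten clinical outcomes and applies Kaplan-Meier, log-rank and Cox methods to each of them. Stroke or TIA is not one of the ten. The closest is "Hospitalization for ischemic stroke, TIA or systemic embolism". In the table shells, the only similar label is "Hospitalization for ischemic stroke or transient ischemic attack". It appears in Table 7, in the block that ignores diagnosis position, and nowhere else.

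SAP II.D.4 says the outcomes are defined by the codes in Appendix C. Item a of that appendix, ischemic or unknown stroke, includes G45.x, the transient ischemic attack family. TIA has no code item of its own. The appendix says its list is not final.

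**The concern.** A secondary endpoint that is named first and has stated power should lead to one defined outcome, one model and one row in the results tables. Here it does not. A programmer working from II.D.4, Tables 7 and 8 and Appendix C would produce no result labelled stroke or TIA. The result labelled stroke would contain TIA.

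The distributed design makes this more costly than usual. Under SAP II.A and II.D.4, patient-level data stay with the Data Partners for all or most analyses, and the sites return results for the listed outcomes. SAP Appendix D.1 describes the meta-analytic approach as the least flexible for subgroup and sensitivity analyses. Once the programs have been run, a missing or mislabelled outcome would need another round at five sites, possibly after other results are known. Several near-miss composites, two diagnosis-position blocks and no multiplicity adjustment (SAP II) are further reasons to settle in advance which row is the endpoint.

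**Working it through.** **1. Labels compared.** The target is stroke or TIA without systemic embolism. The table shows what each candidate contains, by its label alone.

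| Candidate | Ischemic | Hemorrhagic | TIA | Systemic embolism | Where it appears |
|---|---|---|---|---|---|
| Ischemic stroke, TIA or embolism | yes | no | yes | yes | II.D.4; both blocks of Tables 7 and 8 |
| Ischemic or hemorrhagic stroke | yes | yes | no | no | II.D.4; both blocks of Tables 7 and 8 |
| Ischemic stroke or TIA | yes | no | yes | no | Table 7, any-position block only |
| TIA alone | no | no | yes | no | II.D.4; Table 7 principal block; both blocks of Table 8 |

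By label, no row combines all stroke with TIA. The third candidate gives counts, cumulative incidence and a p-value, because Table 7 has no hazard-ratio column. It sits where Table 8 has TIA alone, so it may be a labelling error for that row.

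**2. The same rows with the Appendix C codes.** Item a is I63.x, I67.81, I67.82, I67.89, I67.9 and G45.x. Item b, hemorrhagic stroke, is I60.x to I62.x. The combined ischemic-or-hemorrhagic stroke row is therefore item a or item b, which includes TIA. Its content is close to secondary endpoint 1, while its label is that of secondary endpoint 2. Protocol XV item 5 requires endpoint 2 to exclude TIA, and no all-stroke row does so.

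**3. Partial repairs.**
- Moving only G45.x out of item a makes the combined stroke row correct for endpoint 2, but leaves endpoint 1 with no row.
- Adding only a stroke-or-TIA row, with G45.x still in item a, makes endpoints 1 and 2 the same set of codes.

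Both changes are needed together.

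**4. Stated power reproduced.** Inputs from SAP I.G.2 are one-year rates of 18% untreated and 7% treated; uptake of 33% in the delayed arm and 38% or 40.5% in the early arm; two-sided alpha 0.05; and 30% attrition. Allocation is 1:1.
- Delayed arm: 0.67 × 18% + 0.33 × 7% = 14.37%
- Early arm, 38% uptake: 0.62 × 18% + 0.38 × 7% = 13.82%, a difference of 0.55 points
- Early arm, 40.5% uptake: 0.595 × 18% + 0.405 × 7% = 13.545%, a difference of 0.825 points
- Evaluable patients: 80,000 × 0.70 = 56,000, or n = 28,000 per arm
- Power = Φ(Δ / √[2p̄(1 − p̄)/n] − 1.96), with p̄ the mean of the two rates
- 38% uptake: Φ(0.0055/0.00294 − 1.96) = 46.4%, against 46% stated
- 40.5% uptake: Φ(0.00825/0.00293 − 1.96) = 80.4%, against 80% stated

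Both figures reproduce. Adding a row changes neither.

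**5. How different the two endpoints are on the plan's own figures.** SAP I.G.2 plans for a control-arm one-year rate of 14.4% for stroke or TIA. For stroke it plans for 4.2%, from 5% × (1 − 0.5 × 0.33) = 4.175%. The ratio is 14.4/4.2, about 3.4. These are planning assumptions and may come from different sources, so the ratio is only indicative. It does show that the sponsor does not regard the two endpoints as interchangeable.

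**The case against.** The case against has four parts.

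- **The protocol fills the gap.** The SAP is to be read with the protocol, and protocol XVI.C lists stroke or TIA and prescribes event rates, log-rank tests and Cox models. This stands as far as intent goes: the analysis is pre-specified across the two documents. It does not give the sites an outcome to run, because the list and the table shells in the SAP omit it.
- **A hazard ratio would exist.** On the written codes, the combined stroke row in Table 8 covers ischemic, unknown and hemorrhagic stroke plus TIA. This also stands, so it would be wrong to say that no approximating estimate is returned. It would carry the wrong label, and it would take the place of the stroke-without-TIA endpoint.
- **Stroke may mean ischemic stroke only.** The protocol never says outright. XV item 5 sets stroke or TIA against stroke without TIA, and XVI.C lists ischemic, hemorrhagic and combined stroke separately, which favors all stroke. On the ischemic-only reading, the Table 7 any-position row is the endpoint. It would still have no hazard ratio, no principal-diagnosis result and no place in II.D.4.
- **Appendix C is not final.** True, so a correction is expected. Correcting the codes alone still leaves endpoint 1 without a row (step 3).

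A reader might go further and infer that the composite without hemorrhagic stroke would be used as the substitute, tilting the stroke result toward the intervention. The documents do not support this. Nothing says that any substitute would be used. Hemorrhagic stroke, combined stroke and any bleeding each have their own row and hazard ratio, so an increase would be visible. The documents give no hemorrhagic share from which to size such an effect.

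**Conclusion.** The concern holds as a defect of endpoint specification. The first secondary endpoint is absent by name from all ten outcomes in SAP II.D.4, from Table 8 and from the principal-diagnosis block of Table 7. Appendix C as written puts TIA into the row that should measure stroke without TIA. Following the plan literally therefore mislabels one endpoint and leaves the other without a row of its own.

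The codes and the missing row do not depend on how stroke is read. That stroke includes hemorrhagic stroke is an inference from protocol XV and XVI.C, and the sponsor should confirm it. That G45.x is in item a by mistake is likely, since TIA is also a separate outcome, but the documents do not say so.

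The primary endpoint and the stated power are unaffected. No claim is made about the direction of any bias. The change should be made before the distributed programs run.

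**What to change.** Make these changes together:

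1. Move G45.x out of Appendix C item a into a separate TIA code item.
2. State that stroke in secondary endpoints 1 and 2 means ischemic, unknown or hemorrhagic stroke, as protocol XV and XVI.C suggest, or state otherwise.
3. Add hospitalization for stroke or TIA, first event, to SAP II.D.4 and to both blocks of Tables 7 and 8, labelled secondary endpoint 1. State which diagnosis position is primary. The note under Table 8 restricts it to principal diagnoses although the table has an any-position block, so reconcile the two.
4. Label the combined ischemic-or-hemorrhagic stroke outcome, without G45.x, secondary endpoint 2. Mark the systemic embolism composites as additional outcomes.
5. Change the Table 7 any-position row for ischemic stroke or TIA to TIA alone, to match Table 8.

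The cost is SAP wording, one code-list split and one more outcome in the distributed program. No new data are needed. The downside is one more row per Data Partner in each block.
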